Annex Table 1-5 (cont'd) Other comorbidity

Disease description	ICD-10 code	ICPC code
Hypertension and hypertensive heart disease	I10-I15	K85 Elevated blood pressure (excl. K86-K87) K86 Hypertension without organ damage K87 Hypertension with organ damage
Diseases of arteries, arterioles, and capillaries	I70-I79, and peripheral arterial revascularisation procedures	K91 Atherosclerosis (excl. K76, K90) K92 Atherosclerosis/PVD
Peripheral arterial revascularisation procedures	List of codes to be developed according to each database dictionary	List of codes to be developed according to each database dictionary
Other form of heart diseases	I00-I09, I30-I43, I80-I99	K73 Congenital anomaly cardiovascular K81 Heart/arterial murmur NOS K82 Pulmonary heart disease K83 Heart valve disease NOS K94 Phlebitis/thrombophlebitis K95 Varicose veins of leg K96 Haemorrhoids K99 Cardiovascular disease other
Hyperlipidaemia	E78	T93 Lipid disorder
Diabetes mellitus	E10-E14	T90 Diabetes mellitus
Renal disease	N00-N39	U99 Urinary disease, other
Chronic kidney disease	N18	U99.01 Kidney insufficiency
Other renal disorders	N00-N17, N19, N25-N39	U99 (excl. U99.01)
Anaemias	D50-D64	B78-B83
Peptic ulcer disease	K25-K28	D85 Duodenal ulcer D86 Peptic ulcer other
Liver disease	K70-K77	D97 Liver disease NOS
Osteoporosis	M80-M82	L95 Osteoporosis
Rheumatoid arthritis and other inflammatory arthropathies	M05-M14	L88 Rheumatoid/seropositive arthritis
Systemic connective tissue diseases	M30-M36	No code

Proprietary confidential information © 2017 Boehringer Ingelheim International GmbH or one or more of its affiliated companies

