Annex Table 1-5 Other comorbidity

Disease description	ICD-10 code	ICPC code
Cardiovascular diseases	I00-I99	K73-K99
Ischaemic heart disease	I20-I25 or coronary reperfusion surgery and procedures	
Stable angina pectoris	I20.1, I20.8, I20.9	K74.02 Stable angina pectoris
Unstable angina pectoris	I20.0	K74.01 Unstable angina pectoris
Acute myocardial infarction	I21	K75 Acute myocardial infarction
Other acute or subacute ischaemic heart disease	I22-I24	K76 Ischaemic heart disease w/o angina
Chronic ischaemic heart disease	I25	No specific code
Coronary reperfusion surgery and procedures	List of codes to be developed according to each database dictionary	List of codes to be developed according to each database dictionary
Arrhythmias	I47-I49	K78-K80
Paroxysmal tachycardia	I47	K79 Paroxysmal tachycardia
Ventricular tachycardia	I47.0, I47.2	No specific code
Supraventricular tachycardia and unspecified	I47.1, I47.9	No specific code
Atrial fibrillation and flutter	I48	K78 Atrial fibrillation/flutter
Other cardiac arrhythmias	I49	K80 Ectopic beats all types
Ventricular fibrillation and flutter	I49.0	No specific code
Other cardiac arrhythmias	I49.1-I49.9	No specific code
Conduction disorders	I44-I45	K84 Heart disease other
Cardiac arrest	I46	No specific code
Heart failure	I50	K77 Heart failure
Cerebrovascular disease	I60-I69, G45	K89-K90
Cerebral haemorrhage (subarachnoid, intracerebral, other non-traumatic)	I60-I62	K89 Transient cerebral ischaemia
Cerebral infarction and stroke	I63, I64, G46.5	K90 Stroke/cerebrovascular accident
Transient ischaemic attack	G45	K89 Transient cerebral ischaemia
Other cerebrovascular disease and sequelae of cerebrovascular disease	I65-I69	No specific code

Proprietary confidential information © 2017 Boehringer Ingelheim International GmbH or one or more of its affiliated companies

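### In the ICPC column of SAP Annex Table 1-5, raised blood pressure (K85) counts as hypertension, and K74 without a subcode has no angina row (PHARMO-GP only; minor)

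*SAP*

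**What the plan says.** SAP Section 5.3.5 takes comorbidities from diagnoses recorded at any time before or on the index date, using Annex Table 1-5, and leaves additional database-specific detail to Section 9.2. SAP Section 7.2 presents the annex table as the full code list. SAP Table 3 shows that ICPC is used only for primary care in PHARMO-GP; Denmark codes in ICD-10 and the French source maps to ICD-10.

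Three parts of the ICPC column matter here:

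- **Hypertension and hypertensive heart disease** (I10-I15). The ICPC cell lists "K85 Elevated blood pressure (excl. K86-K87", then "K86 Hypertension without organ damage", then K87 (hypertension with organ damage).
- **Angina.** The stable row (I20.1, I20.8, I20.9) has "K74.02 Stable angina pectoris" and the unstable row (I20.0) has "K74.01 Unstable angina pectoris". The ICPC cell of the parent row, ischaemic heart disease, appears blank. The cardiovascular total is K73-K99.
- **Renal disease** (N00-N39). The ICPC code is "U99 Urinary disease, other". The chronic kidney disease row has "U99.01 Kidney insufficiency", and the other renal disorders row has "U99 (excl. U99.01".

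SAP Sections 5.3 and 6.5 treat a condition with no matching code as absent, not as missing.

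**The concern.** Describing recorded baseline characteristics of new olodaterol users is a primary objective (SAP Section 3), with a secondary counterpart for indacaterol. These rows supply the medical history tables for both drugs (SAP Section 7.2, Shell Tables 5.1-5.3 and 6.1-6.3).

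A row headed hypertension that admits a code defined as not hypertension does not measure what its heading says. An angina split that accepts only two subcodes has nowhere to put an angina record lacking one. Because an unmatched record is coded as disease absent, that loss would not show up as missing data. A reader of the tables could not detect either problem.

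**Working it through.** The plan states no prevalence for these conditions, so there is no figure to reproduce. The check is to trace which rows each code enters when the annex is applied literally.

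| GP record in PHARMO-GP | Rows entered through the ICPC cells |
|---|---|
| K85 | Hypertension; cardiovascular total |
| K86 or K87 | Hypertension; cardiovascular total |
| K74.01 | Unstable angina; cardiovascular total |
| K74.02 | Stable angina; cardiovascular total |
| K74, no subcode | Cardiovascular total only |
| U99.01 | Renal disease; chronic kidney disease |
| Other U99 | Renal disease; other renal disorders |

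**Hypertension.** Within this row, K86 and K87 carry the hypertension labels, and K85 excludes both. The patients added by K85 are those with K85 and none of K86, K87 or a linked hospital code in I10-I15. Call their share k and the share with diagnosed hypertension h. The row reports h + k, and since k cannot be negative the error has one direction. With assumed values, since the documents give none:

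- h = 20%, k = 1%: reported 21%; relative excess 1/20 = 5%.
- h = 20%, k = 10%: reported 30%; relative excess 10/20 = 50%.
- h = 40%, k = 1%: reported 41%; relative excess 1/40 = 2.5%.
- h = 40%, k = 10%: reported 50%; relative excess 10/40 = 25%.

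**Angina.** The protocol (Annex Table 4:1) used I20 as a whole. The SAP splits it and gives I20.9 a place under stable angina. In the protocol's own respiratory code tables the .9 entries (J44.9, J45.9) are the unspecified forms; by analogy I20.9 is the ICD-10 counterpart of K74 without a subcode. The ICPC cells have no such counterpart. The same table shows that the gap can be closed, because the U99 rows provide for entries outside a named subcode. If a share a of patients has GP-recorded angina and a fraction u of them carry only K74 without a subcode, the two angina rows together show a(1 - u). With assumed a = 8%:

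- u = 25%: 8% x 0.75 = 6%.
- u = 75%: 8% x 0.25 = 2%.

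If the apparently blank ischaemic heart disease cell means the sum of its sub-rows (K74.01, K74.02, K75, K76), K74 without a subcode is missing from that row too.

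**Renal.** The whole ICPC definition of renal disease is one residual urinary code. The paired ICD-10 cell is the broad block N00-N39. Nothing in the documents shows whether U99 is wider or narrower than that block, so no direction of error can be derived. The chronic kidney disease row uses U99.01 alone and is not inflated by the rest of U99.

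**The case against.** The strongest defence is that Section 9.2 may hold the operative PHARMO definitions. That cannot be checked, and the point is conditional on it. It is only a partial answer: SAP Section 7.2 calls the annex the complete list and Section 5.3.5 assigns Section 9.2 only additional detail, so a correct override there would still contradict the annex.

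K85 may have been included deliberately for sensitivity. That is possible, but the row heading and its ICD-10 partner describe diagnosed disease, and a separate row keeps the information without mixing the two.

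For angina, the documents do not say that GPs record K74 without a subcode, linked hospital diagnoses will recover some patients, and the blank parent cell may come from conversion of the table to text. All of this stands and limits the likely size. It does not give such a record an angina row.

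A reader might infer four stronger conclusions that the documents do not support:

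- **Angina records are lost altogether.** They are not: K74 is still counted in K73-K99.
- **Renal disease is overstated.** The direction is not shown, for the reason given in the working.
- **The ICD-10 renal rows are miscounted because N20-N24 is in no sub-row.** The parent is N00-N39 and the other renal disorders sub-row is "N00-N17, N19, N25-N39", with N18 separate. Patients with N20-N24 are still counted in the parent, and other parents in the table, such as I00-I99, also exceed their sub-rows.
- **Code choice alone would create a difference between PHARMO-GP and Denmark.** SAP Table 2 shows that Denmark has no GP diagnoses, so the sources would differ whatever ICPC codes are used. Protocol Section 9.7 also analyses each database separately.

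**Conclusion.** The point holds as a minor code-list defect in PHARMO-GP, conditional on Section 9.2 not overriding the annex. The K85 rule is wrong on the table's own labels and can only raise the count of diagnosed hypertension. The K74 rule leaves a gap in the angina rows; whether the gap matters depends on how often GPs omit the subcode, which is an assumption. The U99 issue is one of labelling only.

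The size of each error is unknown, because the documents contain no code frequencies and the percentages above are illustrations. The damage is confined to a few descriptive rows in one subset of one source. Off-label prevalence, the main outcome, uses other codes (SAP Table 5) and is unaffected. Olodaterol and indacaterol users in PHARMO-GP are classified with the same list.

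**What to change.** Edit the ICPC column of Annex Table 1-5, and check that Section 9.2 agrees with it:

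1. Restrict the hypertension row to K86-K87. Report K85 in a separate row for elevated blood pressure without a hypertension diagnosis, counting there only patients with no hypertension code.
2. Enter K74 excluding K74.01 in the stable angina row, to match the placement of I20.9, and enter K74-K76 in the ischaemic heart disease row.
3. For PHARMO-GP, keep U99.01 as chronic kidney disease and label the rest of U99 as other urinary disease.

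The cost is a code-list edit with no new data. The downside of the first change is that a few true hypertensives coded only K85 leave the hypertension row; they remain visible in the new row. The second change treats unspecified angina as stable, as the ICD-10 column already does with I20.9, and a footnote should say so.

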Annex Table 4:1 (con't) Other comorbidity

| Disease Description  | ICD-10 Code  | ICD-9 Code   |
|---|---|---|
| Cardiovascular diseases  | I00-I99  | 390-459  |
| Cerebral infarction and stroke  | I63, I64, G46.5   | 433.1, 434.1, 436   |
| Transient ischaemic attack  | G45   | 435   |
| Other cerebrovascular disease and sequelae of cerebrovascular disease | I65-I69   | 433.0, 434.0, 437, 438  |
| Hypertension and hypertensive heart disease                           | I10-I15   | 401-405   |
| Diseases of arteries, arterioles, and capillaries                     | I70-I79, and peripheral arterial revascularisation procedures       | 440-449 and peripheral arterial revascularisation procedures        |
| Peripheral arterial revascularisation procedures                      | List of codes to be developed according to each database dictionary | List of codes to be developed according to each database dictionary |
| Other form of heart diseases  | I00-I09, I30-I43, I80-I99   | 390-398, 420-425, 429, 440-459                                      |
| Hyperlipidaemia  | E78  | 272  |
| Diabetes mellitus  | E10-E14  | 250  |
| Renal disease  | N00-N39  | 580-599  |
| Chronic kidney disease  | N18   | 585   |
| Other renal disorders   | N00-N17, N19, N25-N39   |   |
| Anaemias   | D50-D64  | 280-285  |
| Nutritional anaemias  | D50-D53   | 280-281   |
| Iron deficiency anaemias  | D50   | 280   |
| Other anaemias  | D55-D64   | 282-285   |
| Peptic ulcer disease   | K25-K28  | 531-534  |
| Liver disease  | K70-K77  | 570-573  |
| Osteoporosis   | M80-M82  | 733.0  |
| Rheumatoid arthritis and other inflammatory arthropathies      | M05-M14  | 712-714, 716, 696.0  |
| Systemic connective tissue diseases                            | M30-M36  | 710  |
| Malignancy   | C00-C97  | 140-209  |
| Depressive disorders   | F32-F33  | 311,   |
| Pregnancy (at the index date)                                  | O00-O48  | 630-649  |

ICD-10 = *International Statistical Classification of Diseases and Related Health Problems, 10th Revision*; ICD-9 = *International Classification of Diseases, 9th Revision*.

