General practitioner outpatient diagnoses	Yes, in data subset PHARMO-GP ¹	No	Yes (a panel of 1,200 general practitioners) ²
Specialist diagnoses	Yes, those in the hospital (no outpatient hospital or non-hospital clinics) or as communicated to and recorded by the GP in PHARMO-GP (primary care)	Yes, those in the hospital (inpatient diagnosis) and hospital outpatient clinics (outpatient diagnosis) (not outside the hospital)	Yes (a panel of 40 pulmonologists) ³
Pharmacy-dispensed medications	Yes	Yes	No
Prescribed medications	Yes, in data subset PHARMO-GP ¹	No	Yes

GP = General Practitioner; IMS = IMS Health Information Solutions; PHARMO = PHARMO Database Network; RWE LPD = Real-World Evidence Longitudinal Patient Database.

- 1 For this study, data from the Out-patient Pharmacy Database and the Hospitalisation Database are available for the overall source population (approximately 4 million patients covered); the subcohort PHARMO-GP includes approximately 1 million patients with data in the Out-patient Pharmacy Database, the Hospitalisation Database, and the General Practitioner (GP) Database. The Out-patient Pharmacy Database will be used to identify medication use.
- 2 The GP panel covers a population of approximately 1.8 million active patients.
- 3 The pulmonologist panel covers a population of approximately 55,000 active patients.

The coding of diagnoses, procedures, and medications varies across databases ([Table 3](#)).

Proprietary confidential information © 2017 Boehringer Ingelheim International GmbH or one or more of its affiliated companies

Table 3 Types of diagnosis, procedures, and medication codes in the study databases

Type of code	PHARMO, The Netherlands	National Registers, Denmark	IMS RWE LPD, France
Diagnoses	Hospital: ICD-10 ¹ Primary health care: ICPC ²	ICD-10	Local in-house thesaurus that can be mapped to ICD-10
Procedures	CBV	NCSP version 1.16, 2012	Local in-house thesaurus that can be mapped to ICD-10
Medications	ATC	ATC	/ EphMRA mapped to ATC

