ATC = Anatomical Therapeutic Chemical; CBV = Centraal Beheer Verrichtingenbestand (codes), Dutch Hospital Data Foundation–owned registration system for procedures, which links to the Dutch Healthcare Authority (NZa) declaration codes and the Dutch Classification of Procedures; EphMRA = European Pharmaceutical Market Research Association; ICD-9 = *International Classification of Diseases, 9th Revision*; ICD-10 = *International Statistical Classification of Diseases and Related Health Problems, 10th Revision*; ICPC = International Classification of Primary Care; IMS = IMS Health Information Solutions; NCSP = *Nordic Medico-Statistical Committee's Classification of Surgical Procedures*; PHARMO = PHARMO Database Network; RWE LPD = Real-World Evidence Longitudinal Patient Database.

- 1 Hospital codes in PHARMO before 2011 were ICD-9 and CBV. PHARMO will work with ICD-9 codes and map them to ICD-10 codes before conducting the analysis.
- 2 Available for PHARMO-GP, a data subset of PHARMO with information from GPs.

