5.3.5 Other comorbidities

Characterisation of the patient population will include a description of the medical history of comorbidities listed in [Annex Table 1-5](#), which will be identified through recorded diagnosis at any time before or on the index date. Additional details on database-specific specifications are described in Section [9.2](#).

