7.2 CONCOMITANT DISEASES AND MEDICATION

Frequency of history of specific diseases and conditions of interest at any time before the index date will be assessed for each exposure group in each data source within the overall study population (Shell Table 5.1 and Shell Table 6.1). The same analysis will be repeated for adults (Shell Table 5.2 and Shell Table 6.2) and for those patients aged 40 years or older with a diagnosis of COPD (Shell Table 5.3 and Shell Table 6.3). Diagnosis of COPD, asthma, and other respiratory comorbidities and time since first COPD diagnosis will be included as part of the description of medical history. In this table, COPD, asthma, and respiratory comorbidities will not be mutually exclusive, and a patient will be allowed to be in more than one group. The comorbidities to be considered are listed in Sections [5.3.4](#) and [5.3.5](#), and a complete list of codes is included in [Annex Table 1-5](#).

The number and percentage of patients with a prescription or dispensing for a specific medication within the year before the index date will be described in each exposure group for the overall population (Shell Table 7.1 and Shell Table 8.1), for all adults (Shell Table 7.2 and Shell Table 8.2), and for those patients aged 40 years or older with a diagnosis of COPD (Shell Table 7.3 and Shell Table 8.3). A description of the medications considered is detailed in Section [5.3.6](#), and the list of codes is presented in [Annex Table 1-6](#).

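### SAP Annex Table 1-5: ICD-10 codes G45 and G46.5 fall outside their parent rows, and ICPC K82 has no ICD-10 counterpart in its own sub-row

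*SAP*

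**What the plan says.** SAP Section 7.2 plans the frequency of each listed comorbidity overall, in adults, and in patients aged 40 or older with COPD. Of the codes it says "and a complete list of codes is included in" Annex Table 1-5. Section 5.3.5 adds: "Additional details on database-specific specifications are described in Section" 9.2, which is not in the text available for review.

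In the cardiovascular block of that annex, the row for TIA is ICD-10 G45 or ICPC "K89 Transient cerebral ischaemia". In *Other form of heart diseases* the ICD-10 cell reads "I00-I09, I30-I43, I80-I99", and the ICPC cell includes "K82 Pulmonary heart disease".

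SAP Table 3 shows where each coding system applies. ICPC is marked "Available for PHARMO-GP, a data subset of PHARMO with information from GPs". Denmark and PHARMO hospital data use ICD-10, and the French source has a "Local in-house thesaurus that can be mapped to ICD-10".

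Sections 5.3 and 6.5 state the rule for absent codes: a patient with no listed code is treated as not having the condition.

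**The concern.** Describing the baseline characteristics of new olodaterol users is a primary objective, and cardiovascular history is a large block of that description. A reader of the table will expect anyone counted in a child row to be counted in its parent, and will expect the ICD-10 and ICPC cells of one row to mean the same condition. Neither holds for the codes at issue.

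Because absence of a listed code means absence of the disease, an omitted code produces a false negative and not a missing value. Nothing in the output would flag it. The coding system follows the data source, so the discrepancy could be taken for a small difference between populations.

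**Working it through.** The plan gives no figure to reproduce. The check expands the ICD-10 and ICPC diagnosis ranges in the cardiovascular block and compares each parent with its children. Procedure lists, which the annex leaves to each database, are not part of it.

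**1. Child codes outside the parent (ICD-10).**

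| Row | ICD-10 | Inside I00-I99? | Inside I60-I69, G45? |
|---|---|---|---|
| Transient ischaemic attack | G45 | No | Yes |
| Cerebral infarction and stroke | I63, I64 | Yes | Yes |
| Cerebral infarction and stroke | G46.5 | No | No |

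G45 and G46.5 are the only sub-row codes outside the parent. In the ICPC column no sub-row code lies outside K73-K99. K89 is inside both K89-K90 (cerebrovascular) and K73-K99.

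**2. Parent codes in no sub-row (ICD-10).** From I00-I99 take I00-I09, I10-I15, I20-I25, I30-I43, I44-I45, I46, I47-I49, I50, I60-I69, I70-I79 and I80-I99. What remains is I16-I19, I26-I29 and I51-I59. The residual heart row therefore has K82 under ICPC but nothing from I26-I29 under ICD-10. The documents show this gap but do not label it. That pulmonary heart disease is I26-I28 comes from the ICD-10 classification itself.

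**3. Three patients traced through the rows.**

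| Only vascular code | Cardiovascular parent | Cerebrovascular | Specific sub-row |
|---|---|---|---|
| G45 (ICD-10) | No | Yes | TIA: yes |
| K89 (ICPC) | Yes | Yes | TIA: yes |
| G46.5 (ICD-10) | No | No | Stroke: yes |
| K90 (ICPC, stroke) | Yes | Yes | Stroke: yes |
| I26-I28 (ICD-10) | Yes | n/a | None |
| K82 (ICPC) | Yes | n/a | Other form of heart diseases: yes |

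**4. Cross-check with the protocol.** Protocol Annex Table 4:1 carries the same ICD-10 strings. In its ICD-9 column, TIA (435) is inside the parent 390-459, so the TIA break is specific to ICD-10. The residual row there reads "390-398, 420-425, 429, 440-459", which leaves 415-417 in no sub-row, so the sub-row gap also exists under ICD-9. SAP Table 3 says PHARMO hospital codes from before 2011 are mapped from ICD-9 to ICD-10 before analysis. The protocol pairs 435 with G45, so a record mapped that way would leave the parent.

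**5. Size.** The shortfall in the ICD-10 cardiovascular parent is the share of new users whose vascular codes are all G45 or G46.5. Anyone who also has an I-code is counted. The shortfall in the residual heart row is the share with a code in I26-I28 and none in that row's listed ranges. The documents give neither share.

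**6. After the edits.** With G45 and G46.5 in the cardiovascular parent and G46.5 in the cerebrovascular row, no sub-row diagnosis code lies outside its parent. With I26-I28 and the optional I51-I52 in the residual row, only I16-I19, I29 and I53-I59 remain in no sub-row.

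**The case against.** Several points on the other side stand.

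- The SAP nowhere says that sub-rows must exhaust the parent. The absence of I26-I29 is a gap in itemisation and not a nesting failure, because those codes are inside I00-I99. What remains wrong is narrower: one row lists the condition under ICPC and not under ICD-10.
- Section 9.2 may adapt the lists by source. That lowers certainty about what will be programmed. It does not repair a core annex that Section 7.2 presents as complete.
- Differences between sources have larger documented causes: Denmark has no general practitioner diagnoses and France no hospital diagnoses (SAP Table 2). Protocol Section 9.7 has every analysis run separately by database with no statistical inference. Within a source, olodaterol and indacaterol users are described with the same list.

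A reader might infer that these patients are counted in PHARMO-GP and missed altogether in the other sources. The documents do not support that. A G45-only patient is still counted in the TIA and cerebrovascular rows, and an I26-I28 patient is still counted in the cardiovascular parent.

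**Conclusion.** The point holds as a minor inconsistency in the code lists. G45 is outside the ICD-10 cardiovascular parent, G46.5 is outside both that parent and the cerebrovascular row, and K82 has no ICD-10 match in its sub-row. The first two follow from the annex alone. The third rests on reading pulmonary heart disease as I26-I28 in the classification the SAP uses.

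Followed literally, the annex gives wrong counts in individual rows of the baseline comorbidity tables. No percentage can be attached, because it would rest wholly on assumed prevalences. The off-label classification does not use these rows and is unaffected.

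**What to change.** In the ICD-10 column of SAP Annex Table 1-5:

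- Set *Cardiovascular diseases* to I00-I99, G45, G46.5.
- Set *Cerebrovascular disease* to I60-I69, G45, G46.5.
- Add I26-I28 to *Other form of heart diseases*, to match K82. Adding I51-I52 there is optional and serves coverage only.

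Make the same edits in protocol Annex Table 4:1 so that the two documents stay aligned, and check them against the source-specific definitions in Section 9.2.

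These edits do not make the ICD-10 and ICPC columns equivalent. K84, labelled as other heart disease, stays in the conduction row; K88, K93, K97 and K98 stay in no sub-row; and several ICD-10 rows have no ICPC code. A table footnote should say so.

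The cost is an edit to two annexes and the matching programs, with no new data and no change to the main analysis.
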